4.3.2 Lenvatinib

In this protocol, lenvatinib at 8 mg daily dose will be combined with pembrolizumab and either CAPOX or mFOLFOX6. Lenvatinib has been studied in combination with chemotherapy in NSCLC. In the Phase 1 dose-escalation study, lenvatinib was combined with paclitaxel (200 mg/m2) followed by 1-hour infusion of carboplatin (AUC 6.0 min mg/mL). Twenty-eight patients were treated for which there were 2 DLTs. A MTD was defined as 4 mg BID (equivalent to 8 mg daily). Even at the 4 mg BID dosing, efficacy remained impressive with an ORR 68.2% (95% CI 45.1-86.1), and DCR of 90.9% (95% CI 70.8-98.9) [Nishio, M., et al 2013].

LEAP-006 is an ongoing Phase 3, randomized, double-blind study of first-line pembrolizumab plus platinum doublet chemotherapy (pemetrexed and platinum) +/- lenvatinib (8 mg qd) in participants with metastatic NSCLC. In this study, the regimen was tolerable with fewer than 3 DLTs occurring in each platinum-containing arm. The ORR was 69.2% [Nishio, M., et al 2020]. Part 2 randomized portion of the study is ongoing. Based on the data from the LEAP-006 study, 8 mg is likely to be safe and effective when used in combination with pembrolizumab and chemotherapy.

During the Consolidation Phase, lenvatinib at 20 mg oral daily will be given in combination with pembrolizumab without chemotherapy. In the KEYNOTE-146/Study 111 (NCT02501096) Phase 1b/2 study of lenvatinib plus pembrolizumab in solid tumors, TRAEs were reported in 97% of patients. Treatment-related AEs resulted in lenvatinib dose reduction and/or interruption in 85%, lenvatinib discontinuation in 13%, pembrolizumab dose interruption (45%) and pembrolizumab discontinuation (15%). The most common AEs reported as reasons for lenvatinib dose reduction and/or interruption were fatigue (26%), diarrhea (23%), hypertension (17%), decreased appetite (16%), and proteinuria (11%) [Taylor, M. H., et al 2020].

In an open-label Phase 1b/2 study of lenvatinib plus pembrolizumab in participants with advanced gastric cancer many patients were treated with the combination therapy at 20 mg daily dose of lenvatinib. TRAE led to dose interruptions in 28 patients (97%) and at least 1 dose reduction of lenvatinib in 29 patients (100%); 1 level dose reduction (14 mg) in 9 patients (31%), 2 level (10 mg) in 14 patients (48%), 3 level (8 mg) in 5 patients (17%) and 4 level (4 mg) in 1 patient (3%) [Kawazoe, A., et al 2020a]. As described in the background, noninferiority of lower dose lenvatinib has been studied in approved indications of DTC and RCC, showing that lower dosages of lenvatinib have failed to show noninferiority to higher approved dosing. These studies suggest that maximizing the dose of lenvatinib may be important for best long-term outcomes [Brose, M. S., et al 2020] [Pal, S., et al 2020]. Based on these data, during Consolidation Phase, the starting dose of lenvatinib will be 20 mg oral daily combined with pembrolizumab 400 mg every 6 weeks. Dose escalation schema in this study is defined such that only patients who tolerate 8-mg dose during induction would be eligible to escalate the lenvatinib dose. We expect that some participants will subsequently

need dose reduction due to toxicity but understand that maximizing the lenvatinib the dose may confer better long-term outcomes.

A 21-day Safety Run-in in Part 1 will include approximately 12 participants, and these participants will start on an 8 mg dose of lenvatinib (see Section 4.1 for details). For those participants who do not tolerate 8 mg during the Induction Phase or 20 mg during the Consolidation Phase due to severe hypersensitivity and/or Grade 3 or higher ongoing AEs, dose reduction/discontinuation/dose escalation/dose reescalation will occur as described in detail in Section 6.6.3.

4.3.3 Maximum Dose/Exposure of Lenvatinib and Pembrolizumab for This Study

The maximum dose/exposure of lenvatinib in this study is lenvatinib 8 mg qd for 12 weeks in the Induction Phase, followed by lenvatinib 20 mg qd during the Consolidation Phase for up to 2 years. The maximum dose/exposure of pembrolizumab allowed in this study is 400 mg Q6W for 18 infusions in the First Course (approximately 2 years), and 9 infusions (approximately 1 year) in the Second Course.

Participants may continue treatment with lenvatinib if they experience clinical benefit according to the PI with Sponsor consultation until disease progression or unacceptable toxicity.

4.3.4 Background Chemotherapy

Participants randomized to the lenvatinib plus pembrolizumab plus chemotherapy arm will receive either 4 cycles of CAPOX OR 6 cycles of mFOLFOX6 given concurrently with lenvatinib and pembrolizumab concurrently during the Induction Phase. Participants randomized to this treatment arm will receive lenvatinib and pembrolizumab in the Consolidation Phase unless either drug is discontinued according to dose modification criteria due to AEs. Participants will NOT receive chemotherapy during the Consolidation Phase if randomized to this arm of therapy. Participants who are randomized to the chemotherapy arm will continue chemotherapy with either CAPOX or mFOLFOX6 per local SOC, consistent with NCCN guidelines for the treatment of first-line advanced/metastatic gastric cancer. The decision to treat with CAPOX or mFOLFOX6 is per investigator judgment and made on a participant-by-participant basis. For any treatment regimen, once the participant is randomized, the chemotherapy (backbone) cannot be changed. Country-specific requirements are noted in Appendix 7.

4.3.4.1 **CAPOX**

Dose determination for capecitabine and oxaliplatin in the CAPOX regimen is in accordance with prescribing information for gastric cancer as described in their package inserts.

In this protocol, the dose regimen will be oxaliplatin (130 mg/m2 IV) on Day 1 and Day 22 of each treatment cycle plus capecitabine (1000 mg/m2 orally twice daily) on Days 1 to 14, and Days 22 to 35 of each treatment cycle (Q3W).

The combination of capecitabine, oxaliplatin, and pembrolizumab is currently being evaluated in an investigator-initiated study in the United States. This study is a single arm, Phase 2 study investigating the combination of pembrolizumab, oxaliplatin, and capecitabine in the first-line treatment of metastatic/recurrent adenocarcinoma of the esophagus or stomach and is being conducted at Duke University (KeyLargo study). Enrollment began in January 2018. The doses of capecitabine, oxaliplatin, and pembrolizumab used are identical to those used in this protocol.

4.3.4.2 mFOLFOX6

Dose determination for oxaliplatin, leucovorin, 5-FU in the mFOLFOX6 regimen is in accordance with prescribing information for gastric cancer as described in their package inserts.

In this protocol, the dose regimen will be oxaliplatin (85 mg/m2 IV) plus leucovorin 400 mg/m2 IV) plus 5-FU (400 mg/m2) IV bolus and 5-FU (2400 mg/m2) IV on Day 1 of each chemotherapy cycle (Q2W).

The choice of the platinum agent used for treatment for gastric cancer in first-line therapy has changed during the last 2 to 3 years in the Group of 7 countries (US, Germany, UK, France, Spain, Italy, Japan) and other countries. Oxaliplatin combinations are now the broad SOC in most countries (mFOLFOX6: 5-FU plus oxaliplatin plus leucovorin), moving away from the nephrotoxicity of cisplatin-based regimens (predominantly cisplatin + 5-FU). The advantages of mFOLFOX6 regimen include elimination of several hours of IV hydration needed to avoid cisplatin nephrotoxicity, and less nausea, vomiting, thromboembolic events and anemia. The SOC chemotherapy predominantly used in the US is mFOLFOX6 (leucovorin plus 5-FU plus oxaliplatin) in first-line gastric cancer.

In a Phase 2 study (HCRN GI14-186), pembrolizumab has been combined with mFOLFOX6 in colorectal cancer using the dose regimen described in this current protocol and was found to show tolerable toxicity. The rate of Grade 3/4 toxicity associated with mFOLFOX6/pembrolizumab was 36.7%. No Grade 5 toxicity was seen on study. The DMC recommended modification of the chemotherapy regimen to oxaliplatin 68 mg/m2, leucovorin 400 mg/m2, 5-FU 320 mg/m2, 5-FU infusion of 1920 mg/m2 over 46 hours based on initial findings that suggested increased neutropenia [Shahda, S., et al 2017].

However, in a subsequent KEYNOTE-651 study, investigating pembrolizumab plus mFOLFOX (Cohort B) in participants with metastatic colorectal cancer, the same regimen without any dose reduction was determined to be safe and tolerable, with the most common Grade 3 TRAEs being anemia and neutrophil count decreased (13% each) [Kim, R., et al 2019].

4.4 Beginning and End-of-Study Definition

The overall study begins when the first participant (or their legally acceptable representative) provides documented informed consent. The overall study ends when the last participant completes the last study-related contact, withdraws consent, or is lost to follow-up (Section 7.3). For purposes of analysis and reporting, the overall study ends when the Sponsor

MK-7902-015-08 FINAL PROTOCOL 10-JUN-2025

receives the last laboratory test result or at the time of final contact with the last participant, whichever comes last.

If the study includes countries in the European Economic Area (EEA), the local start of the study in the EEA is defined as First Site Ready (FSR) in any Member State.

The Sponsor estimates that the maximum duration of the study from first participant entered through long-term follow-up will be 5 years (~1 year after study intervention has been completed) to attain the final assessment of the study (eg, to evaluate safety and/or long-term efficacy) for all evaluable participants. Refer to the Synopsis, Section 1.1, for the duration of participation of participants.

4.4.1 Clinical Criteria for Early Study Termination

The clinical study may be terminated early if the extent (incidence and/or severity) of emerging effects/clinical endpoints is such that the risk/benefit ratio to the study population as a whole is unacceptable. In addition, further recruitment in the study or at (a) particular study site(s) may be stopped due to insufficient compliance with the protocol, GCP, and/or other applicable regulatory requirements, procedure-related problems or the number of discontinuations for administrative reasons is too high.

PROTOCOL/AMENDMENT NO.: 015-08

5 STUDY POPULATION

As stated in the Code of Conduct for Clinical Trials (Appendix 1.1), this study includes participants of varying age (as applicable), race, ethnicity, and sex (as applicable). The collection and use of these demographic data will follow all local laws and participant confidentiality guidelines while supporting the study of the disease, its related factors, and the IMP under investigation.

87

Prospective approval of protocol deviations to recruitment and enrollment criteria, also known as protocol waivers or exemptions, is not permitted.

5.1 Inclusion Criteria

An individual is eligible for inclusion in the study if the individual meets all of the following criteria:

Type of Participant and Disease Characteristics

1. Has histologically and/or cytologically confirmed diagnosis of previously untreated, locally advanced unresectable or metastatic gastroesophageal adenocarcinoma.

Note: Participants who are eligible for radiotherapy or neoadjuvant therapy are not eligible.

- 2. Is not expected to require tumor resection during the treatment course.
- 3. Has gastroesophageal adenocarcinoma that is not HER-2/neu positive.

Note: Participants with gastroesophageal adenocarcinoma that is known to be HER-2/neu positive are not eligible. If HER-2/neu status is unknown, site should follow local standards if HER-2/neu testing is required as SOC.

Country-specific requirements are provided in Appendix 7.

4. Has measurable disease as defined by RECIST 1.1 by scan with IV contrast as determined by the local site investigator. Lesions situated in a previously irradiated area are considered measurable if progression has been showed in such lesions since the completion of radiation (by scans with contrast).

Demographics

08ZFCS

5. Is male or female at least 18 years of age inclusive at the time of signing the informed consent.

PRODUCT: MK-7902 PROTOCOL/AMENDMENT NO.: 015-08

88

Male Participants

6. Male participants are eligible to participate if they agree to the following during the intervention period and for at least 7 days after last dose of lenvatinib or 90 days after last dose of chemotherapy, whichever comes last:

Refrain from donating sperm

PLUS either:

Be abstinent from heterosexual intercourse as their preferred and usual lifestyle (abstinent on a long-term and persistent basis) and agree to remain abstinent

OR

- Must agree to use contraception as detailed below unless confirmed to be azoospermic (vasectomized or secondary to medical cause [Appendix 5]):
- Agree to use a male condom plus partner use of an additional contraceptive method when having penile-vaginal intercourse with a WOCBP who is not currently pregnant. Note: Men with a pregnant or breastfeeding partner must agree to remain abstinent from penilevaginal intercourse or use a male condom during each episode of penile-vaginal penetration.

Please note that 7 days after lenvatinib is stopped, if the participant is on pembrolizumab only, no male contraception measures are needed.

Contraceptive use by men should be consistent with local regulations regarding the methods of contraception for those participating in clinical studies. If the contraception requirements in the local label for any of the study drugs is more stringent than the requirements above, the local label requirements should be followed.

Country-specific requirements are listed in Appendix 7.

Female Participants

- 7. A female participant is eligible to participate if she is not pregnant or breastfeeding, and at least one of the following conditions applies:
- Is not a WOCBP

OR

89

Is a WOCBP and using a contraceptive method that is highly effective (with a failure rate of <1% per year), with low user dependency, or be abstinent from heterosexual intercourse as their preferred and usual lifestyle (abstinent on a long-term and persistent basis), as described in Appendix 5 during the intervention period through 120 days after last dose of pembrolizumab, 30 days after last dose of lenvatinib, or 180 days after last dose of chemotherapy, whichever occurs last, or not to donate eggs (ova, oocytes) to others or freeze/store for her own use for the purpose of reproduction during this period. The investigator should evaluate the potential for contraceptive method failure (ie, noncompliance, recently initiated) in relationship to the first dose of study intervention.

- A WOCBP must have a negative highly sensitive pregnancy test ([urine or serum] as required by local regulations) within 24 hours for urine or 72 hours for serum before the first dose of study intervention.
- If a urine test cannot be confirmed as negative (eg, an ambiguous result), a serum pregnancy test is required. In such cases, the participant must be excluded from participation if the serum pregnancy result is positive.
- Additional requirements for pregnancy testing during and after study intervention are in Appendix 2.
- Abstains from breastfeeding during the study intervention period and for at least 120 days after pembrolizumab or 30 days after cessation of lenvatinib, or 180 days after chemotherapy, whichever occurs last.

The investigator is responsible for review of medical history, menstrual history, and recent sexual activity to decrease the risk for inclusion of a woman with an early undetected pregnancy.

Contraceptive use by women should be consistent with local regulations regarding the methods of contraception for those participating in clinical studies. If the contraception requirements in the local label for any of the study drugs is more stringent than the requirements above, the local label requirements should be followed.

Informed Consent

8. The participant (or legally acceptable representative) has provided documented informed consent/assent for the study.

Additional Categories

- 9. Has a performance status of 0 or 1 on the ECOG Performance Scale within 3 days prior to the first dose of study treatment.
- 10. Has provided a tumor tissue sample for PD-L1 and MSI biomarker analysis. If the initial tissue is inadequate for the analysis, an additional specimen will need to be provided.

- 11. Has adequately controlled BP with or without antihypertensive medications, defined as $BP \le 150/90$ mm Hg and no change in antihypertensive medications within 1 week prior to randomization.
- 12. Has adequate organ function as defined in the following table (Table 3). Specimens must be collected within 10 days prior to the start of study intervention.

Table 3 Adequate Organ Function Laboratory Values

System	Laboratory Value
Hematological	
Absolute neutrophil count (ANC)	≥1500 /mcL
Platelets	≥100,000 /mcL
Hemoglobin	≥9 g/dL or ≥5.6 mmol/L ^a
Renal	
Calculated ^b creatinine clearance	≥50 mL/min
Hepatic	
Total bilirubin	≤1.5 X ULN OR Direct bilirubin ≤ ULN for participants with total bilirubin levels >1.5 ULN
AST (SGOT) and ALT (SGPT)	≤2.5 X ULN OR ≤5 X ULN for participants with liver metastases
Albumin ^c	≥3.0 g/dL
Coagulation	
International Normalized Ratio (INR) or Prothrombin Time (PT) Activated Partial Thromboplastin Time (aPTT)	≤1.5 X ULN unless participant is receiving anticoagulant therapy as long as PT or PTT is within therapeutic range of intended use of anticoagulants ≤1.5 X ULN unless participant is receiving anticoagulant therapy as long as PT or PTT is within therapeutic range of intended use of anticoagulants

ALT (SGPT)=alanine aminotransferase (serum glutamic pyruvic transaminase); AST (SGOT)=aspartate aminotransferase (serum glutamic oxaloacetic transaminase); GFR=glomerular filtration rate; ULN=upper limit of normal.

$$\frac{\text{(140-age [years]} \times \text{weight [kg])}}{\text{Serum creatinine (mg/dL)} \times 72} (\times \text{ F})^*$$

Note: This table includes eligibility-defining laboratory value requirements for treatment; laboratory value requirements should be adapted according to local regulations and guidelines for the administration of specific chemotherapies.

^a Criteria must be met without erythropoietin dependency and without packed red blood cell (pRBC) transfusion within last 2 weeks and G-SCF and thrombopoietin within last 3 weeks.

^b Estimated creatinine clearance using Cockcroft-Gault:

^{*}where F = 0.85 for females and F = 1 for males

^c Criteria must be met without albumin supplementation within the last 72 hours.

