6.6 Dose Modification (Escalation/Titration/Other)

Adverse events will be graded using NCI CTCAE v5.0. Investigators will decide the probability of the event being related to one or more drugs as to whether dose modification of one or more drugs is required.

This is an open-label protocol with a novel combination of pembrolizumab, lenvatinib, and chemotherapy (CAPOX or mFOLFOX6). Because of the multiple agents included in this protocol, overlapping toxicities may occur and the determination of the contribution of agents to specific toxicities may be challenging. Dose modifications can be handled individually or in concert depending on determined relatedness. Refer to Section 6.6.2, Section 6.6.3 and Section 6.6.4 for guidance with regards to dose interruption, dose modification, and overlapping toxicities. Please contact the Sponsor for additional guidance if needed.

Participants who interrupt or discontinue one of the study medications (pembrolizumab, lenvatinib, or chemotherapy) due to toxicity may continue with the other drug(s) in the combination until the criteria for treatment discontinuation are met (eg, unacceptable toxicity, disease progression).

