6.6.3.12 Management of Gastrointestinal Perforation or Fistula Formation

Participants with gastric cancer are at increased risk for GI perforation and fistula formation. Lenvatinib should be discontinued in any participants who develop GI perforation of any grade or Grade 4 fistula.

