	Sepsis/septic shock	Discontinue	Discontinue
Hemolytic uremic syndrome OR any signs of microangiopathic hemolytic anemia		Discontinue permanently	
	Other \geq Grade 3 related organ toxicity ^d	Reduction from 85 mg/m ² to 75 mg/m ²	Reduce by 20%

PROTOCOL/AMENDMENT NO.: 015-08

Category	Toxicity Grade	Oxaliplatin ^a	5-FU
----------	----------------	--------------------------	-------------

5-FU=fluorouracil; ALT=alanine aminotransferase; AST=aspartate aminotransferase; RPLS=reversible posterior leukoencephalopathy syndrome; ULN=upper limit of normal

Further dose reduction may be considered on Sponsor's approval.

Do not retreat until the ANC \ge 1.5 x 10⁹/L and the platelets \ge 75-100 x 10⁹/L, GI and neurotoxicities have resolved and other nonhematologic toxicities \le Grade 1.

- a May consider restarting when neutrophil count resolves to ≥1000/mm³ per local guidance.
- b Discontinue if sepsis/septic shock.
- c Transient ≥7days-<1 cycle; persistent ≥1 cycle.
- d For skin toxicity, reduce 5-FU dose only.

For participants in the lenvatinib plus pembrolizumab plus chemotherapy arm: if chemotherapy (CAPOX/mFOLFOX6) is interrupted due to adverse events, the participants may extend the Induction Phase for a maximum of 6 weeks on approval by the Sponsor. The participant should not exceed 4 cycles of CAPOX treatment, or 6 cycles of mFOLFOX6 treatment.

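### Section 5.1 gives some men on pembrolizumab alone two end dates for contraception, and words the egg-donation rule as an alternative to contraception; both are minor wording corrections

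*Combined protocol and SAP*

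**What the plan says.** Criterion 6 in Section 5.1 sets the end of male measures at "at least 7 days after last dose of lenvatinib or 90 days after last dose of chemotherapy, whichever comes last". Refraining from sperm donation is listed first and joined by *plus* to abstinence or contraception. The note after the list reads "7 days after lenvatinib is stopped, if the participant is on pembrolizumab only, no male contraception measures are needed". A following clause says that where the local label of any study drug is "more stringent than the requirements above, the local label requirements should be followed".

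Section 6.6 allows a participant who stops one drug for toxicity to stay on the rest: he "may continue with the other drug(s) in the combination until the criteria for treatment discontinuation are met". Section 4.3.4 excludes chemotherapy from consolidation in Arm 1, so stopping lenvatinib at that stage leaves pembrolizumab alone. Some events end lenvatinib specifically, for example under Section 6.6.3.12: "Lenvatinib should be discontinued in any participants who develop GI perforation of any grade or Grade 4 fistula".

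Criterion 7, for women, defines the contraception or abstinence period and continues "whichever occurs last, or not to donate eggs (ova, oocytes) to others".

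**The concern.** The note reads as a complete release for a man on pembrolizumab only. It repeats the lenvatinib washout and omits the chemotherapy one. A man who stops lenvatinib soon after induction is on pembrolizumab only while still inside the 90 days that the main rule ties to chemotherapy. He then has two end dates, and the more specific sentence gives the earlier one. The note also does not say whether the sperm-donation restriction ends on the same day.

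In criterion 7, agreeing not to donate eggs appears as an alternative to contraception or abstinence, whereas criterion 6 makes the parallel sperm restriction an additional duty. Appendix 5 does not mention egg donation and so does not repair the wording.

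These are operative reproductive-safety instructions, and a partner's pregnancy is reportable under Section 8.4.5.

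**Working it through.** The plan states no figure to reproduce; the check is date arithmetic.

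**Rules.** Let C be the day of the last chemotherapy dose and L the day of the last lenvatinib dose.

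- Main rule: the washouts end at max(L + 7, C + 90).
- Note: release at L + 7, once the man is on pembrolizumab only.
- The two differ when L + 7 < C + 90, that is, when L − C < 83.
- For stops from 7 days before the last chemotherapy dose onward, the gap is (C + 90) − (L + 7) = 83 − (L − C) days. If lenvatinib stopped 7 or more days before the last chemotherapy dose, the gap can reach the full 90 days.

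**Last chemotherapy dose in Arm 1** (42-day cycles, day 1 = C1D1). Capecitabine is given on "Days 1 to 14, and Days 22 to 35 of each treatment cycle" (Section 4.3.4.1) in Cycles 1 and 2, so the last planned dose is C2D35 = 42 + 35 = day 77. The last mFOLFOX6 infusion starts on C2D29 = 42 + 29 = day 71 (Section 1.3.2). If chemotherapy is interrupted for adverse events, "the participants may extend the Induction Phase for a maximum of 6 weeks on approval by the Sponsor" (end of Section 6.6.5.2), which adds up to 42 days.

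| Regimen | C | C + 90 | Conflict if lenvatinib stops before C + 83 |
|---|---|---|---|
| CAPOX, on schedule | 77 | 167 | day 160 |
| mFOLFOX6, on schedule | 71 | 161 | day 154 |
| CAPOX, +42 days | 119 | 209 | day 202 |
| mFOLFOX6, +42 days | 113 | 203 | day 196 |

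**Examples, on schedule.**

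- CAPOX, lenvatinib stopped on day 84: the note releases on day 91, the main rule on day 167; 167 − 91 = 76 days.
- CAPOX, stopped on day 126 (end of Cycle 3): the note releases on day 133; 167 − 133 = 34 days.
- mFOLFOX6, stopped on day 84: the note releases on day 91, the main rule on day 161; 161 − 91 = 70 days.

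**Who is affected.** Arm 1 men, and Part 1 men, who receive the same regimen under the same criterion. Arm 2 men never receive pembrolizumab. Men who must stop both drugs under the liver criteria of Section 6.6.4.1 are not on pembrolizumab only. In France and the United Kingdom (Sections 10.7.2.1 and 10.7.2.4) a 6-month rule after 5-FU or oxaliplatin governs. For CAPOX it counts from the last oxaliplatin, C2D22 = 42 + 22 = day 64, and, with 6 months taken as 180 days, ends at about 64 + 180 = day 244.

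**After the fix.** With a 90-day chemotherapy condition in the note, both sentences give max(L + 7, C + 90), and the gap is 0 days for every L.

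**The case against.** **A harmonised reading exists.** The main rule takes the later date, and the note has a real purpose: without it, a man on long-term pembrolizumab alone would stay bound for the whole treatment period, well after both washouts. On that reading the note says only that pembrolizumab itself needs no male contraception, and a cautious site applies the later date. This shows the likely intent. The sentence as written is still unconditional, and a site can reasonably follow it.

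**Other safeguards apply.** The label clause removes the conflict wherever a local label is stricter; the labels are not in the documents, so how many countries remain is unknown. The France and UK rules settle the date there. Pregnancy reporting normally extends to at least 180 days after chemotherapy (Section 8.4.1, shortened if new anticancer therapy starts) and includes partners, so a pregnancy in the gap would be captured, though not prevented. These points narrow the issue without removing it.

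**It is probably moot.** The latest window closes on day 209, about 7 months in. The interim analysis is planned about 8 months, and the final analysis about 18 months, after the last participant is randomized (Section 9.7.1). Amendment 8 stops efficacy and survival follow-up, which suggests those analyses are past. Section 9.9 states that enrollment is complete. This largely stands and is why the point is graded as minor. The last randomization date is not given, so it remains an inference.

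**The criterion 7 wording is an evident slip** that few sites would take literally. That is fair, and it can no longer affect entry.

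**Conclusion.** The point holds as a minor wording correction. The note in criterion 6 contradicts the main rule for men who stop lenvatinib less than 83 days after their last chemotherapy dose and continue pembrolizumab alone. On the planned schedule that means stops before day 160 (CAPOX) or day 154 (mFOLFOX6). The stops worked through above release a man 34 to 76 days early, and the extreme case is 90 days. Where lenvatinib stops later, the two rules agree. The *or* in criterion 7 is a literal error of the same grade.

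The day counts assume on-schedule dosing, with mFOLFOX6 counted from the day the last infusion starts, and no stricter local label or country rule. The number of men affected is not in the documents; few or none are likely to be in the window now.

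**What to change.** Make the criterion 6 note conditional: a man on pembrolizumab only needs no contraception measures once at least 7 days have passed since lenvatinib **and** at least 90 days, or any longer country-specific or local-label period, since the last chemotherapy dose. State that the sperm-donation restriction ends on the same date. In criterion 7, replace the *or* before the egg-donation restriction with *and agrees*.

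The cost is two short wording changes with no added procedures. They can wait for the next document update and should be made before this text is reused elsewhere. A site letter is needed only if a participant is still inside the window.
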